Appendix 3 Details on Selected Statistical Models

In this section, we present the details on selected statistical models from this Statistical Analysis Plan (SAP).

CONTROL-BASED MEAN IMPUTATION SENSITIVITY ANALYSIS MODEL FROM SECTION 5.3.3

In the analysis using control-based mean imputation, the treatment effect in annualized rate of change is quantified as

$$\hat{\beta}_x[c] = f_{cren}^{comp}(\hat{\beta}_{cren}^{comp} - \hat{\beta}_{pbo,MAR} - c) + c,$$

where f_{cren}^{comp} is the percentage of participants from the crenazumab arm who have the score collected from the end of treatment visit A (ET-A)/end of treatment visit B (ET-B) visit; $\hat{\beta}_{cren}^{comp}$ is the RCRM estimated annualized rate of change when using the data only from the participants from the crenazumab arm who have the primary endpoint collected from the ET-A/ET-B visit; $\hat{\beta}_{pbo,MAR}$ is the RCRM estimated annualized rate of change when using the data only from the participants from the placebo arm; c is a non-positive constant (note that the sign of c is different from Mehrotra et al. (2017) because our primary endpoints are expected to decline over time) which will be addressed in the following paragraph. The variance of this treatment effect estimator is estimated as:

$$\hat{V}(\hat{\beta}_x[c]) = \left(f_{cren}^{comp}(1 - f_{cren}^{comp})N_{cren}^{-1} + (f_{cren}^{comp})^2 \right) (\hat{V}_{cren}^{comp} + \hat{V}_{pbo,MAR}) + \\ \left(f_{cren}^{comp}(1 - f_{cren}^{comp})N_{cren}^{-1}(\hat{\beta}_{cren}^{comp} - \hat{\beta}_{pbo,MAR} - c)^2 \right),$$

where N_{cren} is the number of participants in the crenazumab arm from the mITT population; \hat{V}_{cren}^{comp} is the variance estimate on the RCRM estimated annualized rate of change when using the data only from the participants from the crenazumab arm who have the primary endpoint collected from the ET-A/ET-B visit; $\hat{V}_{pbo,MAR}$ is the variance estimate on the RCRM estimated annualized rate of change when using the data only from the participants from the placebo arm. The degrees of freedom corresponding to \hat{V}_{cren}^{comp} and $\hat{V}_{pbo,MAR}$ using the Kenward and Roger method (Kenward and Roger 1997) are denoted as λ_{cren}^{comp} and $\lambda_{pbo,MAR}$, respectively.

The degrees of freedom of the treatment effect estimator can be calculated as:

$$\lambda[c] = \frac{\left(\hat{V}(\hat{\beta}_x[c]) \right)^2}{\left(\hat{V}_{cren}^{comp} \right)^2 + \left(\hat{V}_{pbo,MAR} \right)^2}.$$

We will then perform the imputation based on $c=0$. This scenario assumes that the mean slope from the participants with missing values from the crenazumab arm is the same as the estimated overall placebo slope. We note that this assumption is already conservative in estimating the treatment effect because it implicitly assumes participants

on treatment will even do worse than an average placebo participant, after dropping out of the study.

DELAYED-START ANALYSIS MODEL FROM SECTION 5.10.1.1

The statistical model for this delayed-start analysis can be written as:

$$Y_{ij} = \alpha + (\text{Randomization Factors})_i + u_{0i} + (\beta + \beta_x I_{x,i} + u_{1i})t_{ij} + (\beta_{x,B/CAST} t_{ij} - \beta_{x,B/OLE} T_i)(1 - I_{x,i})I_{t_{ij} > T_i} + \epsilon_{ij},$$

where β_x quantifies the crenezumab annualized treatment effect in slowing down the disease progression in Period A of Study GN28352 and $\beta_{x,B/OLE}$ quantifies the treatment effect by switching from placebo to crenezumab in Period B of Study GN28352 and the OLE; T_i represents the time of the first endpoint assessment after participant i enters into Study Period B or the OLE.

Due to the common-close design of Study GN28352, mutation carriers will have varied duration of follow-up at the end Study Period of A. To calculate the crenezumab treatment effect at the end of Study Period A, we first calculate the arithmetic mean of duration in Study Period A (last endpoint assessment date – randomization date in Study Period A + 1) among mutation carriers and we call this duration \bar{T}_1 . On average, the treatment benefit in slowing down the disease progression at the end of Study Period A can be written as:

$$\Delta_1 = \beta_x \bar{T}_1.$$

Similarly, we also calculate the arithmetic average of overall duration at the end of the OLE among mutation carriers and we call this duration \bar{T}_2 . The average treatment benefit remained at the end of OLE can be written as:

$$\Delta_2 = (\beta_x - \beta_{x,B/OLE}) \bar{T}_2 + \beta_{x,B/OLE} \bar{T}_1.$$

Note that both \bar{T}_1 and \bar{T}_2 are treated as constants and are estimated from the data. A non-inferiority test with different margins will be applied ([Liu-Seifert et al. 2015](#)). A 90% CI will be calculated for $\Delta_2 - 50\%\Delta_1$ or $\Delta_2 - 30\%\Delta_1$, depending on the specified margin in the test; if the lower limit of the CI is greater than 0, then the H_0 will be rejected, meaning that by the end of the OLE at least 50% (or 30%) of the treatment effect at the end of Study Period A is preserved.

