3. SAMPLE SIZE DETERMINATION

This study will enroll up to 300 participants: up to 200 participants will be enrolled in the carrier cohort and up to 100 participants will be enrolled in the non-carrier cohort. Participants in the carrier cohort will be randomized in a 1:1 randomization ratio to active treatment or placebo. The study was initially powered to compare the mean change from baseline over 260 weeks in the API ADAD Composite Cognitive Test total score between the active treatment group and the placebo group. Assuming a 25% dropout rate with use of two-sided testing at the overall 0.05 level, a placebo group coefficient of variation of 65% for the Week 260 change scores ($= 100\% \times$ standard deviation of

[figure not shown]
placebo participant change scores/mean of placebo participant change scores) and 100 participants per arm, the study will have at least 80% power to detect a true effect of 30% reduction of the mean decline in the API ADAD Composite Cognitive Test total score in the placebo group using a t-test. Participants in the non-carrier cohort will all receive placebo and will be included in the study in order to maintain the genotype blind.

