Next, we show through simulations *to support the proof*. For simplicity, we assume the BP analysis is performed on 2 endpoints X and Y , where the experimental drug has no treatment effect on X but *could have* a treatment effect on Y .

Mimicking study GN28352, we assume the following:

- 84 participants randomized to the placebo arm and 84 participants randomized to the experimental arm, with no dropout
- Endpoints X and Y both follow a normal distribution within each arm
- Within endpoints X and Y , without loss of generality, the standard deviation in both arms is 1
- Endpoint X has no treatment effect and the placebo arm mean is 1/0.65 (protocol CV assumption on API ADAD Composite Cognitive Test total score=0.65)

In the simulation study, we vary the following, which yields 135 scenarios:

- Treatment effect in endpoint Y in RR scale: 0%, 50%, and 100%
- Placebo mean in endpoint Y : 0, 1, 1.5, 2, 10
- *Endpoints X and Y follow a bivariate normal distribution with*
 - Correlation between endpoint X and Y within the placebo group: $\rho_{pbo}=0.1, 0.5, 0.9$
 - Correlation between endpoint X and Y within the treatment group: $\rho_{exp}=0.1, 0.5, 0.9$

The family-wise type I error in this case equals the probability of rejecting the null H_0 in endpoint X . *When there is a treatment effect in endpoint Y , the only scenario where a type I error can happen is when endpoint X is chosen by the BP analysis.* The number of iterations in the simulation study was 100,000. We summarize the simulation results on type I error (along with the probability of choosing endpoint Y *in scenarios where endpoint Y has a treatment effect*) in [Tables 1–3](#).

Table 1 Family-Wise Strong Type I Error, Assuming 0% Treatment Effect in Endpoint Y (Type I Error in the Weak Sense)

		Placebo Mean in Endpoint Y				
		0	1	1.5	2	10
$\rho_{pbo} = 0.1$	$\rho_{exp} = 0.1$	0.05090	0.04968	0.0583	0.04965	0.04862
	$\rho_{exp} = 0.5$	0.04928	0.04963	0.04995	0.05029	0.04983
	$\rho_{exp} = 0.9$	0.05042	0.04981	0.05012	0.04894	0.05068
$\rho_{pbo} = 0.5$	$\rho_{exp} = 0.1$	0.04949	0.04898	0.04953	0.04982	0.05075

		Placebo Mean in Endpoint Y				
	$\rho_{exp} = 0.5$	0.05052	0.05048	0.05014	0.04953	0.04962
	$\rho_{exp} = 0.9$	0.04913	0.05105	0.05016	0.04927	0.04969
$\rho_{pbo} = 0.9$	$\rho_{exp} = 0.1$	0.05074	0.05068	0.05055	0.04959	0.05099
	$\rho_{exp} = 0.5$	0.05010	0.05002	0.05012	0.04951	0.05088
	$\rho_{exp} = 0.9$	0.04969	0.05063	0.04900	0.05004	0.04970

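### The degrees-of-freedom formula for the control-based mean imputation, as it reads in SAP Appendix 3, uses neither of the component degrees of freedom defined for it and cannot exceed about 2 when the slope-difference term is small

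*SAP*

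**What the plan says.** SAP Section 5.3.4 lists control-based mean imputation among the sensitivity analyses for both primary endpoints. It refers to a cited methods paper and to SAP Appendix 3 for details.

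Appendix 3 defines the estimator as f(β_cren − β_pbo − c) + c. Here f "is the percentage of participants from the crenazumab arm who have the score collected" at the end-of-treatment visit, β_cren is the slope among those completers, β_pbo is the placebo slope, and c is set to 0. "The variance of this treatment effect estimator is estimated as"

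V = [f(1−f)/N + f²](V_cren + V_pbo) + [f(1−f)/N](β_cren − β_pbo − c)².

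The df belonging to V_cren and V_pbo, "using the Kenward and Roger method (Kenward and Roger 1997) are denoted as" λ_cren and λ_pbo. The df of the combined estimator follows at once, introduced by "The degrees of freedom of the treatment effect estimator can be calculated as". In the text available it reads "\lambda[c] = \frac{\left(\hat{V}(\hat{\beta}_x[c]) \right)^2}{\left(\hat{V}_{cren}^{comp} \right)^2 + \left(\hat{V}_{pbo,MAR} \right)^2", that is, V² / (V_cren² + V_pbo²). Neither λ appears in that expression or later in the SAP.

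**The concern.** Two quantities are defined immediately before the one formula that would need them, and the formula does not contain them. What is left is a ratio of squared variances. Every term shrinks at the same rate as participants are added, so the ratio carries almost no information about sample size. A degrees-of-freedom value has to carry that information.

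The primary model assumes data are missing at random. This analysis probes that assumption by giving crenezumab non-completers the placebo slope. If Appendix 3 were programmed literally, the t reference would have about 1 df, and a well-supported estimate would appear to fail a prespecified robustness check. A correction made after unblinding could look data-driven.

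**Working it through.** **Is there a figure to reproduce?** No. The documents give no df, completer fraction or component variance for this analysis. The check therefore uses the formula with stated and assumed inputs.

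**Inputs**
- N = 84 per carrier arm, from the Appendix 2 simulation that mimics the study: "84 participants randomized to the placebo arm and 84 participants randomized to the experimental arm, with no dropout".
- c = 0 (Appendix 3).
- f = 0.75 as the low end, from SAP Section 3: "Assuming a 25% dropout rate with use of two-sided testing at the overall 0.05 level". Values up to 1.00 are assumed.
- Assumed: V_cren = 1/(84f) and V_pbo = 1/84 (equal per-person slope variance, whose scale cancels); λ_cren = 84f − 1 and λ_pbo = 83; slope-difference term zero unless stated.
- A two-sided 95% interval, as stated for the primary model.

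**Variance formula.** For a random proportion f independent of the slope difference D, Var[f(D − c)] = f²Var(D) + Var(f)Var(D) + Var(f)(D − c)². With Var(f) = f(1−f)/N and Var(D) = V_cren + V_pbo, this is the SAP's expression. The variance itself is sound.

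**Satterthwaite df.** Write a = f(1−f)/N + f². The sampling variance of V is about a²(2V_cren²/λ_cren + 2V_pbo²/λ_pbo), taking f and the slope difference as fixed. Then df = 2V²/Var(V) = V² / {a²[V_cren²/λ_cren + V_pbo²/λ_pbo]}.

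**Upper limit of the formula as it reads.** With the slope-difference term at zero, V = a(V_cren + V_pbo). Since (x + y)² ≤ 2(x² + y²), the ratio is at most 2a², and a ≤ 1. It therefore cannot exceed 2.

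**Worked case, f = 0.75**
- V_cren = 1/63 = 0.015873; V_pbo = 1/84 = 0.011905; sum 0.027778.
- a = 0.1875/84 + 0.5625 = 0.56473; V = 0.56473 × 0.027778 = 0.015687; V² = 0.00024608.
- As it reads: 0.00024608 / (0.00025195 + 0.00014172) = 0.63 df.
- With the two λ only: 0.00024608 / (0.00025195/62 + 0.00014172/83) = 42.6 df.
- With a² as well: 42.6 / 0.56473² = 133.7 df.

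**Across completer fractions**

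| f | df as it reads | 97.5% t quantile | df, λ only | df, λ and a² | Interval too wide by (vs λ and a²) |
|---|---|---|---|---|---|
| 0.70 | 0.47 | 231 | 30 | 125 | 117 times |
| 0.75 | 0.63 | 57.0 | 43 | 134 | 28.8 times |
| 0.80 | 0.81 | 22.1 | 59 | 142 | 11.2 times |
| 0.85 | 1.04 | 11.6 | 78 | 149 | 5.9 times |
| 0.90 | 1.31 | 7.4 | 103 | 156 | 3.7 times |
| 1.00 | 2.00 | 4.3 | 166 | 166 | 2.2 times |

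For f from 0.75 to 0.90, either corrected df gives a quantile of 1.98 to 2.02.

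**Sample size.** At f = 0.85 the formula as it reads gives 1.042 with 84 per arm, 1.038 with 1,000 and 1.037 with 100,000.

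**p-values.** An estimate 3 standard errors from zero has p = 0.31, 0.20 and 0.15 at f = 0.75, 0.85 and 0.90 as the formula reads (0.095 at f = 1). Either correction gives p of about 0.003 to 0.004.

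**Slope-difference term.** Setting the squared slope difference at 4 to 8 times (V_cren + V_pbo) gives 0.65–0.67 df at f = 0.75 and 1.33–1.34 at f = 0.90. The conclusion does not change.

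**The case against.** The strongest reply is that this may not be an error in the SAP at all. The text was read from PDF by a program, and losing a divisor from a stacked fraction would produce exactly this expression. That the λ are defined just before it suggests they were meant to be there. Another displayed equation shows similar trouble. In SAP Appendix 2 the expected pooled variance carries a 4σ² divisor that is absent from the variance estimator said to follow from it. This stands, and the point must be conditional on the original page. On the other side, the longer variance formula in Appendix 3 came through intact and re-derives correctly, and nothing else in the documents supplies a correct df formula.

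The method is also delegated to a cited paper that is not available here. The a² factor comes from the derivation above and has not been compared with that paper.

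The consequences are narrow. The analysis lies outside the alpha-controlled testing sequence, and its entry in Section 5.3.4, unlike some others, does not expressly promise an interval or p-value. A df near 1 with about 84 per arm might also be noticed in programming.

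Two stronger readings are tempting. A reader might infer that the missing λ alone account for the gap between about 1 df and about 134–156. They do not: restoring them gives about 43–103, and the rest comes from a². A reader might also take 4 to 29 times as a property of the plan. It is not: the documents give none of the completer fractions, variances or component df behind it, and the factor runs from 2.2 at f = 1 to 117 at f = 0.70.

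**Conclusion.** The point holds, conditional on the original page matching the text available. As it reads, the expression omits both component df and the multiplier a², does not grow with sample size, and cannot serve as a degrees-of-freedom value. That conclusion does not depend on the assumed completer fraction; the size of the error does. With 84 per arm, variances proportional to 1/n, component df of n−1 and 75–90% completers, the df is about 0.6–1.3 and the intervals are roughly 29 to 4 times too wide.

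The effect is confined to the confidence interval and p-value of this one sensitivity analysis, for each primary endpoint. A reader might infer that the primary result is at risk. The documents do not support that: the point estimate, the primary random coefficient regression test and the rule for declaring the trial positive do not use this formula.

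**What to change.** First compare the formula with the original SAP page and with the analysis program. If the divisors are present in both, nothing further is needed.

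If they are absent, replace the formula with

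λ[c] = V² / {a²[V_cren²/λ_cren + V_pbo²/λ_pbo]}, where a = f(1−f)/N_cren + f²,

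or state that a normal reference distribution will be used. With about 84 per arm the two choices differ little (1.98 against 1.96 for a 95% interval). Check the a² factor against the cited methods paper at the same time.

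The cost is one formula in the SAP and one line of code. The change should be documented before unblinding.

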5.10.1.1 Delayed-Start Analyses

The delayed-start analysis will be used for all continuous efficacy endpoints that will be collected in Study Period B and the potential OLE study. Since the potential OLE will not be published by the finalization of this SAP, the description in this section is in general terms and does not focus on any specific endpoint. However, statistical testing will be performed only on the API ADAD Composite Cognitive Test total score and the FCSRT Cueing Index. Other continuous efficacy endpoints, including clinical endpoints, fluid biomarkers, and imaging biomarkers, will be considered exploratory and thus, formal statistical testing will not be done.

Figure 4 illustrates the concept of the delayed-start analysis. As shown in the figure, a treatment effect is assumed in Period A of Study GN28352; the disease progression slope of mutation carriers from the Study Period A crenezumab arm is assumed to be the same in Study Period B and in the OLE; the disease progression slope of mutation carriers from the Study Period A placebo group; however, will have a different slope in Study Period B and in the OLE. The statistical model details can be found in

Appendix 3. To control the type I error within the delayed-start analyses, the fixed testing sequence is specified in the following figure. The α level in each testing is a two-sided 0.05. If at any stage the null hypothesis H_0 is not rejected, then the formal testing procedure will stop.

Figure 4 Illustration of Delayed-Start Analyses Using Data from the Beginning of Period A of Study GN28352 to the End of Study Period B or OLE

[figure not shown]
[figure not shown]

Figure 5 Testing Hierarchy for Delayed-Start Analyses

API = Alzheimer's Prevention Initiative; ADAD = autosomal-dominant Alzheimer's disease; FCSRT = Free and Cued Selective Reminding Task.

Note: For a definition of H0 and H1, please see Section 2.

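### The delayed-start model in SAP Appendix 3 prints an undefined second Period B coefficient, so a literal fit does not match the tested contrast Δ2

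*SAP*

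**What the plan says.** SAP Section 5.10.1.1 sends the reader to Appendix 3 for the delayed-start model. Appendix 3 adds to the primary random coefficient model a term that acts only on participants randomized to placebo, after time T_i. Its bracket and indicators read "\beta_{x,B/CAST} t_{ij} - \beta_{x,B/OLE} T_i)(1 - I_{x,i})I_{t_{ij} > T_i".

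The text below the equation defines a single Period B coefficient. It says that β_x,B/OLE "quantifies the treatment effect by switching from placebo to crenezumab in Period B of Study GN28352 and the OLE", and that T_i "represents the time of the first endpoint assessment after participant" i enters Period B or the OLE. The label CAST is not defined there or in the abbreviation list.

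The two quantities built from the model are "\Delta_1 = \beta_x \bar{T}_1" and "\Delta_2 = (\beta_x - \beta_{x,B/OLE}) \bar{T}_2 + \beta_{x,B/OLE} \bar{T}_1". For the decision, "A 90% CI will be calculated for" Δ2 − 50%Δ1 or Δ2 − 30%Δ1, and the null hypothesis is rejected if the lower limit exceeds zero.

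Section 5.10.1.1 describes the former placebo group only as one that "will have a different slope in Study Period B and in the OLE". It mentions no change of level. It restricts formal testing to the two primary endpoints, in a fixed sequence in which the α "level in each testing is a two-sided 0.05". How that level relates to a 90% interval is a different question, not taken up here.

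**The concern.** The equation, the parameter definition and the contrast should describe one model. They do not. The equation shows two symbols, the definitions cover one, and Δ2 uses that one. A programmer who follows the equation fits two free parameters; one who follows the definitions fits one. The answers can differ.

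This matters because the equation is the governing text for an α-controlled test of retained benefit on both primary endpoints. SAP Section 1 states that the SAP supersedes the protocol's analysis plan. The analysis is triggered two years after the last Period A efficacy visit (Section 5.10.1). By then the sponsor will have been unblinded to analyze Period A (Section 5.10.1.2). Choosing between the two readings at that stage would be an avoidable decision taken with the Period A results known.

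**Working it through.** **Inputs from the documents.** The model term, Δ1, Δ2 and the definition of T_i are in SAP Appendix 3. The intended shape is in Section 5.10.1.1. For the precision check:
- 84 per arm (simulation in SAP Appendix 2)
- Period A from 260 weeks (Section 1.2.1) to about 8 years (Section 5.3.4)
- cognitive visits in Period B at Weeks 25, 53, 77 and 105 (Protocol Appendices 5 and 6)
- CV of 65% for the Week 260 change, and 25% dropout (SAP Section 3)

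The SAP gives no variance components for this model, and no standard error or power for Δ2.

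**Step 1: one coefficient.** Write b for the Period B coefficient and place the switch at T̄1. Apart from the common terms, the means at T̄2 are:
- crenezumab: (β + β_x)T̄2
- former placebo: βT̄2 + b(T̄2 − T̄1)

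The difference is β_xT̄2 − b(T̄2 − T̄1) = (β_x − b)T̄2 + bT̄1. This is the printed Δ2 exactly. The line is continuous, because b(t − T_i) is zero at T_i.

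**Step 2: two coefficients, as printed.** Just after T_i the added term is b_CAST·T_i − b_OLE·T_i, so the former-placebo mean can jump by (b_CAST − b_OLE)T_i. At T̄2 the difference between arms is

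(β_x − b_CAST)T̄2 + b_OLE·T̄1.

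Subtracting the printed Δ2 leaves (b_OLE − b_CAST)T̄2. The printed Δ2 therefore omits b_CAST, which carries the post-switch slope in this version of the model.

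**Step 3: effect on precision.** If the true trajectory is continuous with its knee at T_i, then b_CAST = b_OLE in expectation. The printed Δ2 from a literal fit is then unbiased and only loses precision. The table gives the standard error of Δ2 − 0.5Δ1 from the two-coefficient fit divided by that from the one-coefficient fit. It uses the generalized least squares covariance, with variances calibrated to the 65% CV. The share of that variance due to random slopes is an assumption and is varied.

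| Slope share | Knee at first Period B visit, no dropout | Same, 25% dropout | Knee at end of Period A, no dropout | Same, 25% dropout |
|---|---|---|---|---|
| 10% | 2.28 | 2.22 | 1.94 | 1.86 |
| 25% | 1.97 | 1.89 | 1.62 | 1.55 |
| 50% | 1.57 | 1.52 | 1.31 | 1.28 |
| 75% | 1.27 | 1.24 | 1.13 | 1.12 |
| 90% | 1.10 | 1.10 | 1.05 | 1.04 |
| 95% | 1.05 | 1.05 | 1.02 | 1.02 |

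The excess runs from about 2% to 128%. For Δ2 − 0.3Δ1 the corresponding range is about 1% to 117%. Most of it comes from pairing a two-coefficient fit with a one-coefficient contrast. If the contrast from Step 2 is used with the two-coefficient fit, the excess for Δ2 itself is 0% to 19% under the same calibration.

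**The case against.** The strongest reply is that this is a stray label and the SAP already settles it. Only one coefficient is defined. Section 5.10.1.1 speaks of a changed slope and nothing else. Δ2 is the one-coefficient result. The SC-to-IV switch model in Section 5.3.5 handles the same kind of knee with coefficients on (t_ij − t_i,s). Footnotes in Protocol Appendices 2 and 4 still refer to a continued access study, which CAST may abbreviate, although that is an inference. All of this stands: the single-parameter reading is very probably what was meant.

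Two stronger readings are tempting, and the documents do not support them. A reader might infer that the Δ2 formula is wrong. It is not; it is correct for the only model the SAP defines, and the fault lies in the printed model term. A reader might also infer a definite loss of precision. The documents supply no variance components, and the table runs from negligible to more than double.

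The reply is also right that bias needs unequal coefficients, and that the documents posit no level shift. If a real shift existed, a one-coefficient model would be misspecified too, so the correction should not be presented as a cure for that. Finally, the analysis concerns Period B or the OLE, and Section 5.10 makes Period B analyses exploratory if the study is terminated on the Period A results.

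What remains is that the governing equation, taken as printed, contradicts both its own definitions and the contrast on which the formal decision rests.

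**Conclusion.** The point holds as an inconsistency in the governing model equation, most likely a leftover label. The algebra needs no assumptions: under a literal two-parameter fit the former-placebo line can jump by (b_CAST − b_OLE)T_i, and the benefit implied by the model differs from the printed Δ2 by (b_OLE − b_CAST)T̄2.

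Whether the reported value is biased depends on whether the two coefficients truly differ. With a continuous trajectory and its knee at T_i they do not, and only precision suffers. The range of about 2% to 128% for the standard error of Δ2 − 0.5Δ1 rests on assumed slope shares, 84 per arm, the visit schedule above and the 65% CV. It should be read as showing dependence on those assumptions, not as an estimate for this trial. No inflation of the type I error has been shown. The Period A primary tests are not affected.

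**What to change.** Print the Period B term in SAP Appendix 3 as β_x,B/OLE(t_ij − T_i)(1 − I_x,i)I(t_ij > T_i) and delete β_x,B/CAST. The model is then continuous at T_i, and the equation, the defined parameter and Δ2 agree. This is a one-line correction with no effect on data collection. It should be made before the delayed-start snapshot, so that no choice of reading is left to be made after unblinding.

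The change does not settle a separate matter. T_i is the first endpoint assessment in Period B, which is Week 25 for the cognitive tests, whereas T̄1 is averaged to the last Period A assessment. The knee in the model and the switch time in Δ2 therefore stay roughly half a year apart, and the same amendment could state how that is handled.
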